5.4 DRUG CONCENTRATION MEASUREMENTS AND PHARMACOKINETICS

5.4.1 Assessment of Pharmacokinetics

Plasma concentration monitoring of pirfenidone, nintedanib,

will be performed in order to characterize any potential drug-drug interaction between pirfenidone and nintedanib (see Section 10.2).

Date and exact time points of plasma sampling and drug intake at the clinical site will be documented in the eCRFs by the medical personnel.

5.4.2 Methods of sample collection

A detailed description of sample collection and handling is provided in the Lab Manual in the ISF. For quantification of drug plasma concentrations of pirfenidone, nintedanib (BIBF 1120) and its metabolites **and the second sec**

5.5 ASSESSMENT OF EXPLORATORY BIOMARKER(S)

63451-08Trial Protocol Version 4.0Page 54 of 118Proprietary confidential information © 2016 Boehringer Ingelheim International GmbH or one or more of its affiliated companies

Page 55 of 118

Proprietary confidential information © 2016 Boehringer Ingelheim International GmbH or one or more of its affiliated companies

5.6 OTHER ASSESSMENTS

Not applicable.

5.7 APPROPRIATENESS OF MEASUREMENTS

All measurements conducted in the trial are using standard methods.

The pharmacokinetic parameters and measurements outlined in section 5.4 are generally used as measurements to assess drug exposure.

Page 56 of 118

Proprietary confidential information © 2016 Boehringer Ingelheim International GmbH or one or more of its affiliated companies

6. INVESTIGATIONAL PLAN

6.1 **VISIT SCHEDULE**

Informed consent of all study patients will be obtained in compliance with ICH and GCP guidelines and the principles stipulated in the Declaration of Helsinki prior to any study related procedures, including washout of restricted medications.

The study will consist of three sequential periods; a screening period, a PK evaluation period, and the follow-up period.

Screening will be up to 4 weeks (28 days) in duration. The PK evaluation period will be 24 days in Group 1 and 16 days in Group 2 plus a follow up period of 28 days.

All patients are to adhere to the visit schedule as outlined in flowchart 1 and flowchart 2. Some flexibility is allowed in scheduling the visits according to the visit time windows specified. The trial medication dispensed allows for these time windows. All deviations from the planned schedule will be documented. If any visit is to be rescheduled, subsequent visits should follow the previous visit date schedule. No protocol waivers will be given (e.g. sponsor will not grant permission to include a known ineligible patient).

6.2 DETAILS OF TRIAL PROCEDURES AT SELECTED VISITS

6.2.1 Screening period

No study related procedures will be performed until the patient has signed informed consent. The study will be explained to patients and those who meet entry criteria (Section 3.3) will be invited to participate.

Visit 1

• Informed consent

After informed consent is obtained, the following procedures will be performed:

- Patient demographics
- Medical history, including pre-existing conditions
- Assessment of inclusion/exclusion criteria
- Drug and alcohol test performed at site
- Physical examination including height and weight
- Vital signs
- Blood sample for laboratory tests (Section 5.3.3)
- Urine sample for pregnancy test as required for women of childbearing potential
- 12 Lead ECG using standard site equipment
- Spirometry using standard site equipment
- Register screening by emailing the form provided in the ISF to the Sponsor.
- Assess adverse events since informed consent (if obtained on a previous date)

- Review of concomitant therapy including previous medication taken within the last three months. Dose of all medication to be recorded.
- Schedule next visit to occur within 28 days.

6.2.2 Treatment period(s)

Group 1

The PK evaluation period for Group 1 is a minimum of 24 days plus 28 days follow-up and begins at Visit 2.

Visit 2 Day 1

The patient should attend the clinic at approximately 07:00 so that the following assessments can be started before breakfast is given:

- Review concomitant therapy and any adverse events since screening and throughout the day at regular intervals.
- A drug and alcohol test will be done at the clinic.
- Physical examination and vital signs.
- Urine pregnancy test for women of childbearing potential.
- Spirometry
- Reassessment of inclusion/exclusion criteria.
- Pre-dose PK samples should be taken according to PK Flowchart (Group 1; this should be taken prior to the other blood samples).
- •
- Registration of treatment start by emailing the form provided in the ISF to the sponsor.
- One 150 mg nintedanib capsule should be given to the patient at 08:00 during breakfast (See PK Flowchart Group 1).
- PK samples should be taken according to PK Flowchart (Group 1).
- The patient should be given lunch at 12:00 and a snack at 16:00.
- After the 10-hour PK time point PK collection, the patient can leave the clinic and return to the clinic the next day.

Visit 2 Day 2

- The patient must return to the clinic the next morning (Visit 2 Day 2) for the 24 hour time point at 07:55 (See PK Flowchart Group 1).
- AEs and concomitant medications should also be assessed.
- Dispense two wallets of pirfenidone and instruct the patient to begin the uptitration of pirfenidone, the first dose should be given at the clinic with a snack.
- Provide dosing instructions regarding uptitration to the patient.
- Dispense patient diary.
- Schedule Visit 3 for Day 23.
- Other assessments listed for Visit 2 in the PK Flowchart are conducted at Day 1.

Phone call Day 15

At the end of the planned uptitration, there will be a phone call made to the patient, the following assessments should be covered:

- Assessment of adverse events.
- Review concomitant therapy including dose.
- Remind patient to uptitrate to the full dose of three capsules three times a day from the second wallet of pirfenidone. If the patient is not tolerating the full dose then the patient has a six-day time window to reach full dose for 7 consecutive days. If the patient is not tolerating the uptitration then refer to Figure 4.1.4:1 for instructions.
- Remind patient of Visit 3 scheduled for Day 23.
- Remind patient not to take morning dose of study medication on the day of Visit 3 and to bring their study medication with them to the clinic and also the diary card.

Visit 3 Day 23

Once the patient has been on stable, full dose pirfenidone for 7 days (a 6 day window is allowed to ensure 7 consecutive days) they will return to clinic for the next PK day.

The patient should attend the clinic at approximately 07:00 so that the following assessments can be started before breakfast is given:

- Physical examination and vital signs.
- Urine pregnancy test for women of childbearing potential.
- Blood sample for laboratory tests (Section 5.3.3)
- Pre-dose PK samples should be taken according to PK Flowchart (Group 1, this should be taken prior to the other blood samples).
- •
- Spirometry.
- Review concomitant therapy and any adverse events since previous visit and throughout the day at regular intervals.
- Patients will return all unused medication. Medication compliance will be assessed by counting returned (unused) capsules.
- The patient will return the diary card and this will be reviewed to check that the patient has received seven consecutive, stable days of treatment.
- One 150mg nintedanib capsule and three 267 mg pirfenidone capsules should be given to the patient at should be given to the patient at 08:00 during breakfast (See PK Flowchart – Group 1).
- PK samples should be taken according to PK Flowchart (Group 1).
- The patient should be given lunch at 12:00.
- Three 267 mg pirfenidone capsules will be given to the patient at 14:00 along with a snack.
- A snack will also be given to the patient at 16:00.
- After the PK time point at 18:00, the patient can leave the clinic.
- The patient should take the final dose of three 267 mg pirfenidone capsules at home at approximately 20:00 with food and a glass of water.

Visit 3 Day 24

- The patient must return the next morning (Visit 3 Day 24) for the 24 hour PK time point at 07:55 the next day.
- AEs and concomitant medications should also be assessed.
- Other assessments listed for Visit 3 in the PK Flowchart are conducted at Day 23
- No study drugs are given.
- Remind patient of PK FU visit scheduled for 28 days after this visit.

PK Follow-up/ End of Trial

The patient should return to the clinic 28 days or more after Visit 3 Day 24 for their PK Followup/ End of Trial Visit as detailed in section 6.2.3.

Group 2

The PK evaluation period for this group is for a minimum of 16 days plus 28 days follow-up and begins at Visit 2.

Visit 2 Day 1

- Review concomitant therapy and any adverse events since screening.
- A drug and alcohol test will be done at the clinic.
- Physical examination and vital signs.
- Urine pregnancy test for women of childbearing potential.
- Spirometry
- Reassessment of inclusion/exclusion criteria.
- •
- Registration of treatment start by emailing the form provided in the ISF to the sponsor.
- No PK samples are taken on this day.
- Dispense two wallets of pirfenidone and instruct the patient to take 801mg tid, the first dose should be given at the clinic with food and a glass of water.
- Provide patient with dosing instructions.
- Dispense diary.
- Remind patient of Visit 3a scheduled for Day 8.

Visit 3a Day 8

Once the patient has been on stable, full dose pirfenidone for 7 days (a 3 day window is allowed to ensure 7 consecutive days) they will return to clinic for the first PK day.

The patient should attend the clinic at approximately 07:00 so that the following assessments can be started before breakfast is given:

- Physical examination and vital signs.
- Urine pregnancy test for women of childbearing potential.
- Blood sample for laboratory tests (Section 5.3.3)

- Pre-dose PK samples should be taken according to PK Flowchart (Group 2, this should be taken prior to the other blood samples).

•

- Spirometry.
- Review concomitant therapy and any adverse events since previous visit and throughout the day at regular intervals.
- Patients will return all unused medication. Medication compliance will be assessed by counting returned (unused) capsules.
- The patient will return the diary card and this will be reviewed to check that the patient has received seven consecutive, stable days of treatment.
- Three 267 mg pirfenidone capsules should be given to the patient at 08:00 during breakfast (See PK Flowchart Group 2).
- PK samples should be taken according to PK Flowchart (Group 2).
- The patient should be given lunch at 12:00.
- Three 267 mg pirfenidone capsules will be given to the patient at 14:00 with a snack.
- After the PK time point at 14:00, the patient can leave the clinic.
- The patient should be given the remaining pirfenidone from the previous visit and also one new wallet of pirfenidone and one bottle of nintedanib to take home.
- The patient should take the final dose of three 267 mg pirfenidone capsules at home at approximately 20:00 with food and a glass of water.
- The patient should be reminded to take pirfenidone and nintedanib from Day 9 at home for seven consecutive days.
- Remind patient of Visit 3b scheduled for Day 16.

Once the patient has received nintedanib and pirfenidone for 7 consecutive days, they will return to clinic for Visit 3b for the next PK day. If the patient needs to dose reduce the pirfenidone then this is allowed see Section 4.1.4.

Visit 3b Day 16

Once the patient has been on stable, pirfenidone and nintedanib for 7 days (a 3 day window is allowed to ensure 7 consecutive days) they will return to clinic for the next PK day.

The patient should attend the clinic at approximately 07:00 so that the following assessments can be started before breakfast is given:

- Physical examination and vital signs.
- Urine pregnancy test for women of childbearing potential.
- Blood sample for laboratory tests (Section 5.3.3)
- Predose PK samples should be taken according to PK Flowchart (Group 2, this should be taken prior to the other blood samples).
- •
- Spirometry.
- Review concomitant therapy and any adverse events since previous visit and throughout the day at regular intervals.

63451-08Trial Protocol Version 4.0Page 61 of 118Proprietary confidential information © 2016 Boehringer Ingelheim International GmbH or one or more of its affiliated companies

- Patients will return all unused medication. Medication compliance will be assessed by counting returned (unused) capsules.
- The patient will return the diary card and this will be reviewed to check that the patient has received seven consecutive, stable days of treatment.
- One 150mg nintedanib capsule and three 267 mg pirfenidone capsules should be given to the patient at 08:00 during breakfast (See section 10.2; this will be the last study medication that the patient will receive in the PK evaluation period of the trial).
- PK samples should be taken according to PK Flowchart (Group 2).
- The patient should be given lunch at 12:00.
- After the PK time point at 14:00, the patient can leave the clinic.
- No study drugs are given.
- Remind patient of PK FU visit scheduled for 28 days after this visit.

PK Follow-up/ End of Trial

The patient should return to the clinic 28 days or more after Visit 3b Day 16 for their PK Follow-up/ End of Trial Visit as detailed in section 6.2.3.

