AEs and Concomitant therapy ¹⁶	X	X ¹⁷	X	X ¹⁷	Х
Conclusion of PK evaluation period				Х	
Conclusion of subject participation					X ¹⁵

FOOTNOTES – GROUP 1

- 1. The screening period between Visit 1 and 2 should last a maximum of 28 days. Eligible patients can be started on treatment once central lab results have been received and are found to be consistent with eligibility criteria.
- 2. At site discretion, informed consent may be obtained on one day and the remainder of the screening procedures can follow.
- 3. Vital signs to include blood pressure and pulse rate.
- 4. Patient will be dispensed three wallets of pirfenidone. They will use one wallet to uptitrate for 14 days (Day 2 to Day 15) and then the next wallet for the complete dose of 801 mg tid daily (Day 16 to Day 22). On Day 23 the patient should bring their medication into clinic and will be given the morning and the 14:00 of pirfenidone at the clinic. They will take their evening dose at home and this will be their final dose during the PK period. The patient will also be dispensed a single 150mg dose of nintedanib on Day 1 and Day 23. (See Section 4.1.4).
- 5. Patients will be supplied with a diary and a dosing card and they will be asked to document the number of capsules they have taken each day and also to record any adverse events during this period.
- 6. At the end of the 14 day uptitration (Day 15) a call will be made to the patient to check whether there have been any issues with uptitration and when the patient has reached the full dose (the phone call should be documented in the patient notes). The patient will then continue on full dose (801 mg tid) for 7 consecutive days (Day 16 to Day 22) before returning to the clinic for the next PK day (Day 23). The patient would have their final PK sample taken on Day 24.
- 7. Please see separate PK flowchart Group 1 for details during the PK evaluation period Section 10.2.
- 8.
- 9. Urine dipstick pregnancy tests will be provided by central lab and should be performed in all women of childbearing potential.
- 10. If a patient withdraws from the PK evaluation period or does not tolerate uptitration then the patient should be managed according to Figure 4.1.4:1
- 11. The patient will stop all trial medication on Day 23 and have a washout period from study drug until the PK FU visit.
- 12. Spirometry should be conducted using local standard equipment.

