- 13. The uptitration phase between Visit 2 and Visit 3 can be extended by a maximum of 6 days if the patient needs longer to uptitrate or to achieve 7 consecutive stable days at full dose.
- 14.
- 15. At Visit 4 (PK FU) the optional nintedanib Named Patient Programme will be discussed with the patient.
- 16. AEs and concomitant therapy should be checked at regular intervals during the PK days.
- 17. At Visit 2 Day 2 and Visit 3 Day 24 only these procedures need to be done see Section 6.2.2.
- 18. The PK Follow Up visit should occur at least 28 days after last drug intake.
- 19. DLCO testing will be performed once at visit 1 or 2, or during the screening period (visit 1 to visit 2). The results will be corrected for haemoglobin by the site, see section 10.3 for further details.

Page 8 of 118

Proprietary confidential information © 2016 Boehringer Ingelheim International GmbH or one or more of its affiliated companies

FLOW CHART - GROUP 2

Trial Periods	Screening Period ¹	PK ev	aluation pe	eriod ⁹	PK Follow- up Period ¹⁶
Visit	1	2	3 a	3b ¹²	4
Weeks		0	1	2	6
Days	-28 to -1	1	8	16 ¹⁰	44
Time window for visits			+3 days	+3 days	+3 days
Informed consent ²	Х				
Demographics	Х				
Medical history	Х				
Review of in-/exclusion criteria	Х	Х			
Drug and alcohol testing at site	Х	Х			
Physical examination	Х	Х	Х	Х	Х
Vital signs ³	Х	Х	Х	Х	Х
Laboratory tests	Х		Х	Х	Х
Pregnancy test (urine) ⁸	Х	Х	Х	Х	Х
PK sample ⁶			Х	Х	
		Х			
		Х	X ¹³	X ¹³	Х
		Х	X ¹³	X ¹³	
	Х				Х
Spirometry ¹¹	Х	Х	Х	Х	Х
DLCO ¹⁷	Х	$(X)^{17}$			
Register screening / start of treatment	Х	Х			
Dispense trial drugs ⁴		Х	Х	Х	
Collect trial drug & compliance check			Х	Х	
Dispense and/or collect & review diary ⁵		Х	Х		
AEs and Concomitant medication ¹⁵	Х	Х	Х	Х	Х
Conclusion of PK evaluation period				Х	
Conclusion of subject participation					X ¹⁴

FOOTNOTES – GROUP 2

- 1. The screening period between Visit 1 and 2 should last a maximum of 28 days. Eligible patients can be started on treatment once central lab results have been received and are found to be consistent with eligibility criteria.
- 2. At site discretion, informed consent may be obtained on one day and the remainder of the screening procedures can follow.
- 3. Vital signs to include blood pressure, pulse rate and weight.

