4.1.4 Drug assignment and administration of doses for each patient

Drug is dispensed by the investigator, study coordinator or pharmacist, depending on the site structure. If the patient is currently not being treated for IPF at screening and they fulfil the inclusion/exclusion criteria, they will be assigned manually by the study site personnel to Group 1 and if they are a chronic pirfenidone user at screening and they fulfil the inclusion/exclusion criteria they will be assigned manually by the site to Group 2. There will be no IRT used in this trial. Sites will be required to inform the Sponsor of each screening and each start of treatment using the form provided in the ISF. The Sponsor will monitor recruitment to each group and inform sites when recruitment is close to complete.

Group 1

Visit 2 will be over two days. The patient is not required to stay in the clinic overnight between Day 1 and Day 2. At Visit 2, Day 1, eligible patients will receive one 150 mg nintedanib capsule in the clinic in the morning (Table 4.1.4:2 see Flowchart for Group 1 patients and Section 10.2 for timings of dosing and PK samples). This will be given to the patient by the site staff from a nintedanib bottle (this bottle should be kept at clinic and be used for patients who are in Group 1 for the first and second PK day). Gloves should be worn by the person giving the capsule to the patient and the capsule should be tipped out into a pot where the patient can then pick it up and take it. The patient should swallow nintedanib, unchewed, with food and a glass of water at the clinic.

At Visit 2, Day 2, the patient will return to clinic for their 24 hour PK sample (see Section 10.2) and they will be dispensed three wallets of pirfenidone. The patient will take the first dose at the clinic in the morning with food and a glass of water, under supervision and then go home and continue dosing at home. A dosing card will be provided to the patient, which will explain how they should uptitrate during the trial.

The patient will use the first wallet for 14 days titrating according to Table 4.1.4:1. Once the patient has completed the uptitration then they would use the second wallet and take 3 capsules 3

Boehringer Ingelheim 29 July 2016 BI Trial No.: 1199.229 c03463451-08 **Trial Protocol Version 4.0** Page 34 of 118

Proprietary confidential information © 2016 Boehringer Ingelheim International GmbH or one or more of its affiliated companies

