times a day for the next 7 days. Once the patient has had 7 consecutive, stable days on 801 mg tid they would then come to the clinic for the next PK day (Visit 3, Day 23; there is a 6 day window during the uptitration phase and Visit 3. This allows for extending the uptitration if required and ensuring that there are 7 consecutive, stable days at 801 mg tid before the patient returns to clinic for the second PK day Visit 3. The third wallet of pirfenidone can be used if required during this period).

The patient will return to the clinic for Visit 3. They should not take their medication at home, but should bring it to the clinic with them. At the clinic, they will be given their morning dose of 801mg pirfenidone and they will also receive one 150 mg capsule of nintedanib at the clinic with food and a glass of water. They will also be given their second dose of pirfenidone at the clinic at 14:00. They will take their final dose of pirfenidone at 20:00 in the evening at home once they have left the clinic. They should be advised to take this with food and a glass of water. The following day (Visit 3, Day 24), the patient will return to the clinic for their 24 hour PK sample (see Section 10.2). The patient will then have a washout of 28 days where no study medication is taken and then they will return to clinic for the PK Follow-Up visit (see Flowchart).

If the patient does not achieve 7 consecutive, stable days prior to Visit 3 plus the 6 day window then the patient would stop medication and attend the clinic for Visit 3, but would not have the PK samples taken (See Figure 4.1.4:1).

Table 4.1.4:1	Schedule for the titration	phase of pirfenidone	(Group 1)
---------------	----------------------------	----------------------	-----------

Titration Period	Administration	Dose	Total daily Dose
Day 2 to Day 8 of titration	1 capsule tid	267 mg tid	801 mg
Day 9 to Day 15 of titration	2 capsules tid	534 mg tid	1602 mg

Table 4.1.4:2 Quantity of medication kits dispensed to the patient

Group 1

Visit	Nintedanib bottle	Pirfenidone wallet
2	0 (1 capsule given in clinic)	3
3	0 (1 capsule given in clinic)	

Boehringer IngelheimBI Trial No.: 1199.229c03463451-08Trial Protocol Version 4.0

Page 35 of 118

Proprietary confidential information © 2016 Boehringer Ingelheim International GmbH or one or more of its affiliated companies

Table 4.1.4:2Quantity of medication kits dispensed to patient continued

Group 2

Visit	Nintedanib bottle	Pirfenidone wallet
2	0	2
3a	1	1

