4.1.6 Packaging, labelling, and re-supply

The medication kit for nintedanib is a 75cc PE bottle and contains 30 capsules. These will be provided by BI.

Medication kits for pirfenidone will comprise of a blister package of 63 capsules in a blister package (wallet). These will be provided by BI.

For details of packaging and the description of the label, refer to the ISF.

Medication will be provided by the Department of Pharmaceutical Development of Boehringer Ingelheim Pharma GmbH & Co. KG, Biberach, Germany.

No re-supply is planned.

The nintedanib used in the nintedanib Named Patient Programme does not form part of the study supplies.

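### Protocol 6.2.2 dispenses two pirfenidone wallets to Group 1 where three other places say three; two leave an adherent, on-schedule patient 9 capsules short on Day 23, the test PK day

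*Protocol*

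**What the plan says.** The current body of Protocol version 4.0 gives two quantities for one dispensing event, Group 1 at Visit 2 Day 2.

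- **Two wallets.** Section 6.2.2, the visit-by-visit procedure list: "Dispense two wallets of pirfenidone and instruct the patient to begin the uptitration of pirfenidone".
- **Three wallets.** Group 1 flow-chart footnote 4: "Patient will be dispensed three wallets of pirfenidone". Section 4.1.4: "they will be dispensed three wallets of pirfenidone". The Visit 2 row of Table 4.1.4:2 also shows 3.

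Footnote 4 assigns one wallet to the titration (Days 2 to 15) and the next to the full-dose week (Days 16 to 22). For the test day it says "On Day 23 the patient should bring their medication into clinic". Footnote 13 says the titration phase "can be extended by a maximum of 6 days if the patient needs longer to uptitrate" or to reach seven stable full-dose days. Section 4.1.4 says of that same window: "The third wallet of pirfenidone can be used if required during this period". Section 6.1 states that the supply handed out covers the visit windows. Section 4.1.6 puts 63 capsules in a wallet and plans no re-supply, and Table 4.1.4:2 shows no pirfenidone wallet at Visit 3.

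**The concern.** Both quantities cannot be right, and the lower one sits in the list that site staff are likely to work from during the visit. Day 23 supplies the test profile for the Group 1 primary comparison of nintedanib AUC0-tz and Cmax, within patient, against nintedanib alone on Day 1. The three pirfenidone doses that day (morning, 14:00 and 20:00) all fall inside the nintedanib sampling period, which ends just before 24 hours. If those doses were missing, the profile would not measure nintedanib given with pirfenidone as planned.

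There is a second route to a lost profile. If dosed titration days are added, two wallets no longer cover seven full-dose days. For a patient who does not reach those seven days within the window, section 4.1.4 says "then the patient would stop medication and attend the clinic for Visit 3, but would not have the PK samples taken".

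**Working it through.** **Inputs**

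- Capsules per wallet: 63 (section 4.1.6).
- Dosing (synopsis and Table 4.1.1:2): Days 2–8, one capsule three times daily; Days 9–15, two; Days 16–23, three.
- Window before Visit 3: up to 6 extra days (flow-chart footnote 13).

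**Capsules needed on schedule** (days × 3 doses × capsules per dose)

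| Days | Calculation | Capsules | Running total |
|---|---|---|---|
| 2–8 | 7 × 3 × 1 | 21 | 21 |
| 9–15 | 7 × 3 × 2 | 42 | 63 |
| 16–22 | 7 × 3 × 3 | 63 | 126 |
| 23 | 1 × 3 × 3 | 9 | 135 |

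**Three wallets, reproduced.** 3 × 63 = 189. Wallet 1 equals the titration need (63) and wallet 2 equals the full-dose week (63), as footnote 4 assigns them. Wallet 3 covers Day 23 (9) and leaves 189 − 135 = 54 = 6 × 9. That is exactly six further days at full dose, so three wallets satisfy the statement in 6.1 even when all six window days are full-dose days (135 + 54 = 189, none spare).

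**Two wallets, as 6.2.2 has it.** 2 × 63 = 126. Supply ends with the last dose of Day 22, and 135 − 126 = 9 capsules are missing for Day 23. Section 6.2.2 is then at odds with itself, because it also has the patient bring study medication to Visit 3.

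**Two wallets with the window used**

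- One extra dosed titration day at 3 capsules: titration uses 66, and 126 − 66 = 60 remain.
- One extra dosed titration day at 6 capsules: titration uses 69, and 126 − 69 = 57 remain.
- Seven full-dose days need 63, so in either case they cannot be completed.
- Titration on time, with one extra full-dose day before a delayed visit: the first seven full-dose days are covered, and the shortfall over the extra day and the visit day is 135 + 9 − 126 = 18.
- Titration lengthened only by days without dosing: the shortfall stays at 9.

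**The case against.** The strongest reply is that this is a one-word slip in a checklist. The dosing section, the table that sets dispensing quantities and the flow-chart footnote agree on three, and 4.1.4 explains what the third wallet is for. A site reading any of them has the intended number. Staff also give the morning and 14:00 doses on Day 23 and count returned capsules that day, so they would notice a shortage. Section 7.7 plans 16 patients to obtain 12 with both profiles, and allows more to be added if fewer than 12 are obtained. All of this stands, and it makes the harm possible rather than likely. It does not make 6.2.2 correct.

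Some inferences go further than the documents allow:

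- A reader might infer that the dispensing mark at Visit 3 in the flow chart lets the site top up pirfenidone. That row carries footnote 4, which ties Day 23 dispensing to the single nintedanib dose, and Table 4.1.4:2 gives no pirfenidone quantity there.
- A reader might infer the opposite from the absence of planned re-supply: that no spare wallet could be found. The documents are silent on site stock.
- A reader might infer that two wallets always fail the seven stable days. On schedule they cover them exactly; what is missing is Day 23.
- A reader might infer a flaw in the statistical design. The model, endpoints and sample size do not depend on the wallet count.

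**Conclusion.** The inconsistency is real and sits in operative text, and the capsule count identifies 6.2.2 as the wrong entry. Following it leaves 9 of 135 capsules (one full day) missing on the Group 1 test PK day. If titration is extended by even one dosed day, 3 or 6 capsules are missing from the 63 needed for the full-dose week.

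The 9-capsule figure assumes a fully adherent patient, no dosed window days and no extra stock; a patient who missed doses would have capsules left over. The consequence depends on a site following 6.2.2 over the three agreeing places. It is an operational risk to individual test profiles among approximately 16 planned Group 1 patients, and the documents do not show how many, if any, would be affected. It should be corrected because it bears on a primary-endpoint day and costs almost nothing to put right.

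**What to change.** In Protocol 6.2.2, Group 1, Visit 2 Day 2, change *two* to *three* in the pirfenidone dispensing bullet, and notify sites. Leave the Group 2 Visit 2 instruction at two wallets, since it agrees with Table 4.1.4:2 and with footnote 4 of the Group 2 flow chart. The cost is one word and a note to sites. No analysis, endpoint or sample-size text changes.
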